Appendix 1 Schedule of Assessments (cont.)

- ^m Documentation of HIV, HBsAg, HBsAb, HBcAb, and HCV antibody testing is required. The most recent testing must have occurred within 3 months prior to randomization. If such testing has not been done, it must be performed during screening. If a patient has a negative HBsAg test and a positive total HBcAb test at screening, an HBV DNA test must also be performed to determine if the patient has an HBV infection. If a patient has a positive HCV antibody test at screening, an HCV RNA test must also be performed to determine if the patient has an HCV infection.
- ⁿ Blood samples collected to monitor safety will be collected in patients randomized to both arms. Hematology consists of CBC, including RBC count, hemoglobin, hematocrit, WBC count with automated differential (neutrophils, lymphocytes, eosinophils, monocytes, basophils, and other cells), and platelet count. A manual differential can be done if clinically indicated (see Section 4.5.6).
- ^o Serum chemistry includes BUN, creatinine, sodium, potassium, magnesium, chloride, bicarbonate, calcium, phosphorus, glucose, total bilirubin, ALT, AST, alkaline phosphatase, LDH, total protein, and albumin. Serum bicarbonate is not required as a laboratory assessment in the screening or on-study serum measurements in countries where it is not considered a standard chemistry measurement (e.g., Japan).
- ^p PTT is acceptable if aPTT cannot be performed.
- ^q Urinalysis (specific gravity, pH, glucose, protein, ketones, and blood); dipstick is permitted.
- ^r On Day 1 of Cycle 5 and every four cycles thereafter.
- ^s CT of the chest, abdomen, and pelvis with contrast at screening for all patients. MRI of the abdomen and pelvis with a non-contrast CT scan of the chest may be used in patients for whom CT scans with contrast are contraindicated (i.e., patients with contrast allergy or impaired renal clearance). For patients who are eligible on the basis of completely resected metachronous or synchronous lung, adrenal, or soft tissue metastasis, brain imaging is required no more than 4 weeks prior to randomization.
- ^t Baseline sample to be collected on Cycle 1, Day 1 prior to the first dose of study treatment. For patients who show evidence of immune-mediated toxicity, additional samples will be collected, and all samples will be analyzed centrally. Includes CRP, anti-nuclear antibody, anti-double stranded DNA, circulating anti-neutrophil cytoplasmic antibody, and perinuclear anti neutrophil cytoplasmic antibody.
- ^u Whole blood for DNA isolation will be collected from patients who have consented to optional RBR sampling at Cycle 1, Day 1. If, however, the RBR genetic blood sample is not collected during the scheduled visit, it may be collected as soon as possible (after randomization) during the conduct of the clinical study.
- ^v Patients will receive their first dose of study drug the day of randomization, if possible. If this is not possible, the first dose should occur no later than 5 days after randomization. The initial dose of treatment will be delivered over 60 (\pm 15) minutes. If the first infusion is well tolerated, all subsequent infusions may be delivered over 30 (\pm 10) minutes. Study treatment may be continued for a maximum of 16 cycles (or 12 months, whichever occurs first) in the absence of disease recurrence, unacceptable toxicity, withdrawal of consent, or study termination by the Sponsor.

Appendix 1

Schedule of Assessments (cont.)

- ^w Tumor tissue from surgical resection should be of good quality based on total and viable tumor content (sites will be informed if the quality of the submitted specimen is inadequate to determine tumor PD-L1 status). Prior to signing the main consent form for the study, patients may specifically allow for the collection and testing of archival or fresh tumor tissue by signing the prescreening consent form. After signing the Informed Consent Form, retrieval and submission of archival tumor sample can occur outside the 28-day screening period. Representative FFPE tumor specimens in paraffin blocks (blocks preferred) or at least 15 unstained slides of the highest tumor grade portion of the RCC tumor, with an associated pathology report, must be submitted for central testing for determination of sufficient viable tumor content prior to study enrollment. The pathology report should include tumor size, stage (e.g., T3a), nodal status (e.g., N2), Fuhrman Grade 1-4, and presence or absence of tumor necrosis. Fuhrman grade will be assessed by a central laboratory with expert pathologists for monitoring purposes. Eligibility will be determined locally by the investigator.
- ^x All patients will undergo a mandatory tumor biopsy sample collection at the time of radiographic confirmation of disease recurrence (see Section 4.5.5). Acceptable samples include resections; core needle biopsies for deep tumor tissue or lymph nodes; or excisional, incisional, punch, or forceps biopsies for cutaneous, subcutaneous, or mucosal lesions. For core needle biopsy specimens, at least three cores should be submitted for evaluation. Pathology reports should be submitted to the central review facility if available.
- ^y For patients who have consented to collection of optional biopsies on the Optional Collection of Samples for RBR Informed Consent Form, optional tumor biopsy samples may be collected by core needle or excisional/punch biopsy per investigator discretion. Optional biopsy tissue will be stored in the RBR. Not applicable for sites that have not been granted approval for RBR sampling.
- ^z Concomitant medications include any prescription medications or over-the-counter medications. At screening, any medications the patient has used within the 7 days prior to written informed consent should be documented. At subsequent visits, changes to current medications or medications used since the last documentation of medications will be recorded.
- ^{aa} After informed consent has been obtained but prior to randomization, only serious adverse events caused by a protocol-mandated intervention should be reported. Upon randomization into study, patients who experience a serious adverse event or protocol-defined adverse events of special interest will be followed for safety for 90 days following their last dose of study drug or until they receive another systemic anti-cancer therapy, whichever comes first. Patients who experience all other adverse events will be reported for patients until 30 days after the last dose of study, or until initiation of another systemic anti-cancer therapy, whichever occurs first. After this period, investigators should ensure any deaths, serious adverse events, or other adverse events of concern are reported if they are later assessed to be related to study treatment. Post-study treatment follow-up visits for tumor recurrence surveillance should include monitoring for potential late serious adverse events and adverse events of special interest. The investigator should follow each adverse event until the event has resolved to baseline grade or better, the event is assessed as stable by the investigator, the patient is lost to follow-up, or the patient withdraws consent. Every effort should be made to follow all serious adverse events considered to be related to study treatment or study-related procedures until a final outcome can be reported. Any medications given as treatment for an adverse event should be reported, even if given after the Treatment Discontinuation Visit.

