4.3.2 Dosage, Administration, and Compliance

4.3.2.1 Atezolizumab and Placebo

Administration of atezolizumab/placebo will be performed in a setting with emergency medical facilities and staff who are trained to monitor for and respond to medical emergencies. For more detailed information regarding administration, refer to the Atezolizumab Investigator's Brochure and Pharmacy Manual. For anaphylaxis precautions, see [Appendix 8](#). Atezolizumab/placebo infusions will be administered per the instructions outlined in [Table 5](#).

Table 5 Administration of First and Subsequent Atezolizumab/Placebo Infusions

First Infusion	Subsequent Infusions

• Premedication is not routinely recommended prior to the atezolizumab/placebo infusion.• Vital signs (pulse rate, respiratory rate, blood pressure, and temperature) should be measured within 60 minutes prior to the infusion.• Atezolizumab should be infused over 60 (\pm 15) minutes.• If clinically indicated, vital signs should be measured every 15 (\pm 5) minutes during the infusion and at 30 (\pm 10) minutes after the infusion.• Patients should be informed about the possibility of delayed post-infusion symptoms and instructed to contact their study physician if they develop such symptoms.	
• If the patient experienced an infusion-related reaction with any previous infusion, premedication with antihistamines, antipyretics, and/or analgesics may be administered for subsequent doses at the discretion of the investigator.• Vital signs should be measured within 60 minutes prior to the infusion.• Atezolizumab/placebo should be infused over 30 (\pm 10) minutes if the previous infusion was tolerated without an infusion-related reaction, or 60 (\pm 15) minutes if the patient experienced an infusion-related reaction with the previous infusion.• If the patient experienced an infusion-related reaction with the previous infusion or if clinically indicated, vital signs should be measured during the infusion and at 30 (\pm 10) minutes after the infusion.

Guidelines for medical management of IRRs are provided in [Appendix 11](#).

No dose modification for atezolizumab/placebo is allowed. Guidelines for treatment interruption or discontinuation are provided in [Section 5.1.2](#) and in [Appendix 11](#).

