Appendix 1 Schedule of Assessments (cont.)

Study Procedures	Arm A (Atezolizumab) and Arm B (Placebo)				
	Screening for Randomization	All Cycles (1 Cycle=21 Days)	Discontinuation ^a (End of treatment)	Post-Treatment Visit	Follow-Up ^b
	Days -28 to -1	Day 1 (±3 Days for Cycles≥2)	≤ 30 Days after Last Dose	3 Months (±2 Weeks) after Last Study Treatment Dose	
Coagulation panel (aPTT, INR) ^p	x		x	x	
Urinalysis ^q	x	As clinically indicated			
TSH, free T3, free T4	x	x ^{f,r}	x	x	
Imaging assessment ^s	x				
CRP and auto-antibody testing ^t		x ^t			
Serum sample for ADA assessment		See Appendix 2			
Serum sample for PK sampling		See Appendix 2			
Blood samples for biomarkers		See Appendix 2			
Optional whole blood sample for RBR ^u		x (Cycle 1, Day 1) ^u			
Atezolizumab or placebo infusion ^v		x			
Archival/screening FFPE tumor tissue specimen or 15 unstained slides ^w	x				
Fresh biopsy (mandatory sample ^x and optional RBR sample ^y)			At the time of radiographic confirmation of disease recurrence ^{x,y}		
Assessments for RCC recurrence ^h		Every 3 months following randomization (± 2 weeks) in first 3 years; every 6 months (±4 weeks) thereafter until death, disease recurrence, loss to follow-up, or withdrawal of consent.			

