Grade 1 ^a Fever ^b with or without constitutional symptoms	
 • Immediately interrupt infusion. • Upon symptom resolution, wait for 30 minutes and then restart infusion at half the rate being given at the time of event onset. • If the infusion is tolerated at the reduced rate for 30 minutes, the infusion rate may be increased to the original rate. • If symptoms recur, discontinue infusion of this dose. • Administer symptomatic treatment,^c including maintenance of IV fluids for hydration. • In case of rapid decline or prolonged CRS (> 2 days) or in patients with significant symptoms and/or comorbidities, consider managing as per Grade 2. • For subsequent infusions, consider administration of oral premedication with antihistamines, anti-pyretics, and/or analgesics, and monitor closely for IRRs and/or CRS.

Appendix 11 Risks Associated with Atezolizumab and Guidelines for Management of Adverse Events Associated with Atezolizumab (cont.)

Table 7 Management Guidelines for Infusion-Related Reactions and Cytokine-Release Syndrome (cont.)

Event	Management

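### Appendix 1 footnote v permits a 30-minute infusion straight after a reaction if the first infusion was tolerated, where the governing Table 5 calls for 60 minutes

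*Protocol*

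**What the plan says.** The infusion duration appears in two places in the protocol.

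- **Section 4.3.2.1 and Table 5.** The section states: "Atezolizumab/placebo infusions will be administered per the instructions outlined in" Table 5. The table gives the first infusion over 60 (±15) minutes. Each later infusion should run over 30 (±10) "minutes if the previous infusion was tolerated without an infusion-related reaction", or over 60 (±15) "minutes if the patient experienced an infusion-related reaction with the previous infusion".
- **Appendix 1, footnote v.** The footnote hangs on the schedule row "Atezolizumab or placebo infusion". It gives the same 60 (±15) minutes for the first dose and then says: "If the first infusion is well tolerated, all subsequent infusions may be delivered over 30" (±10) minutes. It has no condition for a reaction at a later infusion and does not refer to Table 5.

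Appendix 11, Table 7, deals with managing infusion-related reactions. For Grade 1 and 2 it tells the site to "restart infusion at half the rate being given at the time of event onset", and for later doses it says: "For subsequent infusions, consider administration of oral premedication with antihistamines, anti-pyretics, and/or analgesics", with close monitoring. It gives no duration for the next dose.

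**The concern.** The two texts use different triggers. Table 5 looks at the most recent infusion, so it responds to a reaction whenever one occurs. Footnote v looks only at the first infusion, so once that has gone well, nothing later changes what it allows.

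Infusion-related reactions are a listed risk (Section 5.1.1) and are among the adverse events of special interest (Section 5.2.3). A site that takes the duration from the schedule could give the next dose over 30 minutes to a patient who has just reacted, when the administration instruction wants it slowed to 60. Such a site would also miss the prompt for extra vital signs. Appendix 1 footnote k asks for them during or after the infusion only if clinically indicated, whereas Tables 5 and 6 also trigger them after a reaction or symptoms at the previous infusion.

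What is at stake is the tolerability of single doses. No endpoint or analysis depends on it.

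**Working it through.** The plan gives no figure to reproduce, so the check sets the texts side by side and then asks how far the difference reaches.

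**1. Time windows** (Table 5 and footnote v)

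- 30 ± 10 minutes gives 20–40 minutes.
- 60 ± 15 minutes gives 45–75 minutes.
- Gap: 45 − 40 = 5 minutes. The windows do not overlap, so the tolerances cannot reconcile them.

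**2. Possible histories before the next dose**

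| History | Table 5 | Footnote v | Result |
|---|---|---|---|
| No reaction at any infusion | 20–40 min | 20–40 min permitted | Agree |
| Infusion 1 tolerated, reaction at the previous (later) infusion | 45–75 min | 20–40 min permitted | Conflict |
| Reaction at infusion 1, previous infusion tolerated | 20–40 min | Silent | No conflict; Table 5 applies |
| Reaction at infusion 1, next dose is infusion 2 | 45–75 min | Silent | No conflict; Table 5 applies |

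Only the second row is a conflict. Infusion 2 can never fall in it, because for infusion 2 the first infusion is also the previous one.

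**3. Whether another text settles the duration.** In Appendix 11, Table 7, the half-rate rule applies to restarting the interrupted infusion, not to the next dose. For later doses after Grade 1 or 2, the table offers premedication and monitoring. Its footnote f, on re-challenge after permanent discontinuation, says only that a longer infusion may be considered. None of these sets a duration for the next dose.

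**4. Which patients.** Table 7 calls for permanent discontinuation at Grade 3 or 4, so apart from re-challenge the conflict concerns Grade 1–2 reactions. Grade 2 includes hypotension not needing vasopressors and hypoxia needing low-flow oxygen, and dosing may resume once it resolves.

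**5. Whether any dosing remained at Version 10.** The inputs are:

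- projected accrual of 33 months (protocol Section 6.1.2)
- up to 12 months of treatment (Section 3.1.1)
- Version 10 dated 12 November 2021 (SAP Section 7)

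The dosing span from first randomization is 33 + 12 = 45 months. The documents do not give the date of first randomization, so the dates below are assumptions:

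| Assumed first randomization | Last dosing (+45 months) | Against Version 10 |
|---|---|---|
| 29 March 2017 | 29 December 2020 | Ended about 10.5 months before |
| 12 February 2018 | 12 November 2021 | Ends on that date |
| 12 February 2019 | 12 November 2022 | About 12 months remain |

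Two facts favor the earlier dates. The first independent-review charter is dated 29 March 2017 (SAP Section 7). SAP Section 1.2.3.1 says that in 2019 the team learnt how recurrences were being backdated in central reads, which fits poorly with a first randomization in February 2019. This is inference and does not fix the date. Accrual slower than projected would move the end of dosing later, month for month.

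**The case against.** The strongest reply is that the protocol already resolves the matter. Section 4.3.2.1 makes Table 5 the instruction, and footnote v says only that a shorter infusion may be given. A site that follows Table 5 breaches neither text. Harm would require a site to rely on the schedule footnote, pass over the administration section, and choose the faster option just after a reaction. Section 4.3.2.1 also sends sites to the Investigator's Brochure and Pharmacy Manual for more detail. Neither is available here, so what dosing staff were actually told is unknown.

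Most of this stands, and it is why the point is minor. It does not remove the problem, because the footnote sits on the dosing row of the schedule and permits, without exception, what Table 5 advises against.

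Safeguards also limit the consequence. Table 5 says: "If the patient experienced an infusion-related reaction with the previous infusion or if clinically indicated, vital signs should be measured during the infusion", and again afterwards. It also allows premedication after any earlier reaction. Table 6 has a similar vital-sign trigger, and Table 7 advises close monitoring.

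A reader might also infer a second conflict for a patient who reacted at infusion 1 and tolerated the most recent one, on the ground that the footnote's condition for 30 minutes is then not met. The documents do not support that. The footnote says what is allowed if the first infusion went well and nothing about the alternative, so Table 5's explicit rule applies unopposed.

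Nor is the number of dose positions a measure of size. With at most 16 infusions, a reaction at any of infusions 2–15 (14 positions) could be followed by an affected dose. That counts opportunities and says nothing about how often one arises.

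**Conclusion.** The inconsistency is real, confined to one situation, and minor. For a patient who tolerates infusion 1, has a Grade 1–2 infusion-related reaction at a later infusion and is dosed again, footnote v permits 20–40 minutes where the governing Table 5 calls for 45–75.

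The number of patients affected cannot be computed, because the documents give neither a rate of infusion-related reactions in this trial nor a date of first randomization. On projected accrual, no dose given after Version 10 is affected if first randomization fell on or before 12 February 2018, and the documents lean that way without proving it.

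A reader might infer that patients were in fact infused too fast after a reaction, or that the comparison between arms is disturbed. The documents show no such dosing. The wording is the same for both blinded arms, and efficacy, power and alpha do not depend on it.

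**What to change.** In Appendix 1 footnote v, delete the sentence on infusions after the first and put in its place: *For the duration of subsequent infusions, see Table 5.* Table 5 needs no change.

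If any patient is still being dosed, send this to sites as a memo; otherwise make the correction in the next amendment. The cost is one line of wording, with no effect on data collection, blinding or analysis. If dosing has ended, the change is purely editorial.

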Appendix 1 Schedule of Assessments (cont.)

- ^{bb} Survival follow-up information will be collected via telephone calls, patient medical records, and/or clinic visits approximately every 3 months (± 7 days) until death, loss to follow-up, consent withdrawal, or study termination by the Sponsor. All patients (irrespective of which arm they are randomized to) will be followed for survival and new anti-cancer therapy information (including targeted therapies and immunotherapies) and subsequent progressions, unless the patient requests to be withdrawn from follow-up; this request must be documented in the source documents and signed by the investigator. If a patient withdraws from *the* study, study staff may use a public information source (e.g., county records) to obtain information about survival status.
- ^{cc} The PRO questionnaires (FKSI-19 and EQ-5D-5L) will be completed by the patients at the investigational site while patients are receiving study treatments. All PRO questionnaires completed at the clinic are required to be completed prior to the exchange of meaningful information (e.g., lab results), prior to administration of study treatment and/or prior to any other study assessment(s) that could bias patients' responses to ensure that the validity of the instruments is not compromised and to ensure that data quality meets regulatory requirements. Study personnel should review all questionnaires for completeness before the patient leaves the investigational site, and the hard copy originals of the questionnaires must be maintained as part of the patient's medical record when relevant at the site for source data verification. Study personnel will record patient responses on a paper copy as a record of source documentation.
- ^{dd} Odd-numbered cycles only (i.e., Cycles 1, 3, 5, 7, 9, 11, 13, and 15).
- ^{ee} After discontinuation of the study treatment, the PRO questionnaires will be administered by trained site staff over the phone or at the site at end of treatment visit, the post-treatment visit, any visit for assessment of RCC recurrence, and at two timepoints after disease recurrence during survival follow-up.

Appendix 2 Schedule of Pharmacokinetic, Immunogenicity, and Biomarker Samples

Visit	Timepoint	Sample Type
Cycle 1, Day 1	Pre-dose	Serum atezolizumab ADA Serum atezolizumab pharmacokinetics Plasma PD biomarker Serum PD Biomarker Whole blood PBMC
	30 min (\pm 10 min) (after the end of infusion)	Serum atezolizumab pharmacokinetics
Cycles 2 and 4, Day 1	Pre-dose	Plasma PD biomarker Serum PD biomarker
Cycles 2, 3, and 4, Day 1	Pre-dose	Serum atezolizumab ADA Serum atezolizumab pharmacokinetics
Cycle 8, Day 1	Pre-dose	Serum atezolizumab ADA Serum atezolizumab pharmacokinetics
Treatment discontinuation visit ^a	At visit	Serum atezolizumab ADA Serum atezolizumab pharmacokinetics
	At visit	Plasma PD biomarker Serum PD biomarker
At disease recurrence ^{b, c}	At visit ^d	Plasma PD biomarker Serum PD biomarker

ADA = anti-drug antibody; PBMC = peripheral blood mononuclear cell;
PD = pharmacodynamic.

- ^a Treatment discontinuation visit occurs within 30 days after last dose of study treatment and applies to all patients who discontinue study treatment (regardless of the reason).
- ^b If a patient discontinues the study due to disease recurrence, it is acceptable to collect PD blood at the visit at which tumor assessment shows disease recurrence only, and waive collection at the treatment discontinuation visit.
- ^c Disease recurrence blood sample collection should occur at the same time as disease recurrence tissue biopsy sample collection. Disease recurrence blood sample should still be collected even if the Medical Monitor waives the requirement for tissue biopsy sample.
- ^d It is acceptable to collect the disease recurrence samples at either investigator-assessed recurrence or IRF-assessed disease recurrence. The disease recurrence samples must be collected within 2 weeks after disease recurrence has been confirmed.

